11.6 Dosage schedules

Participants will receive one of three doses:

- Selenase 200mcg
- Selenase 50mcg
- Placebo

Orally, once daily, in the morning

The total duration of treatment will be 26 weeks.

11.7 Dosage modifications

There are no planned dose modifications.

If a participant develop diabetes (fasting glucose $\geq 7.0\text{mmol/l}$) or thyroid dysfunction (TSH outside the reference range and determined as clinically significant by the investigator) during the study (identified on safety monitoring bloods, or a new diagnosis reported by participant at monthly contact), their treatment will be stopped. If a participant experiences other adverse effects thought to be related to IMP the PI will decide if that participant should stop treatment.

11.8 Known drug reactions and interaction with other therapies

Ascorbic acid; absorption of selenium possibly reduced by ascorbic acid (give at least 4 hours apart)

Eltrombopag: selenium possibly reduces absorption of eltrombopag (give at least 4 hours apart)

11.10 Assessment of compliance

Compliance will be assessed by asking at each contact whether participants have missed any doses of treatment. Participants will also be asked to return their study medication bottles for a pill count.

The number of reported missed doses and pill count will be recorded in the CRF.

Patients with less than 75% compliance will continue in the trial and ITT analysis, but will be excluded from per-protocol analysis.

Participants who are non-compliant with the safety monitoring at three months (do not attend or decline to have blood test) will be withdrawn from the trial.

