10. ASSESSMENT AND FOLLOW-UP

10.1 Assessment of efficacy/effectiveness

Efficacy measurements will be obtained at baseline, three months and six months.

Blood samples for biochemical measurements will be taken fasted. The approximate maximum blood sample volume at each visit will be 50ml. Urine samples will be obtained as triplicate samples from fasted second morning voids on three days before or including the study visit, and kept refrigerated until the study visit. Equal volume aliquots from the urine samples will be pooled into a single sample by the study team. Samples will be processed according to a sample handling SOP.

Real-time baseline serum selenium will be measured in the Chemical Pathology laboratory, Sheffield Teaching Hospitals.

All other samples will be frozen at -80°C, and analysed in batches at the end of the study.

Urine NTX/Cr will be measured by automated assay (EC Vitros) in the laboratory of the Sheffield Academic Unit of Bone Metabolism or Chemical Pathology laboratory, Sheffield Teaching Hospitals.

Serum selenium at all time points will be measured by X-ray fluorescence spectroscopy (27), selenoprotein P will be measured by immunoassay (28) and glutathione peroxidase by enzyme analysis by [name], Institute for Experimental Endocrinology, Charité - University Medical School Berlin.

Other biochemical markers of bone turnover (serum CTX, PINP and osteocalcin) will be measured by automated assay in the laboratory of the Sheffield Academic Unit of Bone Metabolism.

HsCRP and IL-6 will be measured by the Sheffield Teaching Hospitals Clinical Immunology laboratory.

Hydroperoxidases will be measured using commercially available manual assay kits in the laboratory of the Sheffield Academic Unit of Bone Metabolism.

Grip strength will be assessed using a digital hand dynamometer (Saehan Corporation, Masan, Korea). Three measurements will be taken and the best value used for analysis. Short physical performance battery (SPPB) score will be calculated from a chair stand and narrow walk test (22). *See Appendix 1 – Physical function tests.*

Height and weight will be measured with an electric scale and stadiometer.

Pulse and blood pressure will be measured with an automated sphygmomanometer (Dynamap).

Bone mineral density will be assessed by DXA of the spine and hip (Hologic) at baseline and six months according to standard scanning protocols, by specialist DXA scan technicians in the Sheffield Clinical Research Facility.

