11.5 Drug storage and supply

IMP will be provided by Sharp Clinical Services as above, specifically for use in this trial.

There are two planned manufacturing runs, to allow for possible changes to total participant number after the interim analysis. Further runs may be added if required based on the final sample size, recruitment time and shelf life of IMP.

Each manufacturing run will be delivered to Sheffield Teaching Hospitals pharmacy, under the supervision of the trial pharmacist.

The IMP will be stored at 15 to 25°C in STH pharmacy. Temperature logs will be maintained by STH pharmacy.

The first bottle of 93 tablets will be dispensed at the baseline visit, and the second bottle of 93 tablets at the 13 week visit. Bottles will be labelled with the study identifier (STH19102) and participant randomisation code.

IMP will be dispensed by pharmacy on receipt of a completed study-specific prescription, signed by the PI or delegated registered doctor.

STH pharmacy will retain dispensing records.

Unused or expired IMP at STH will be sent for hazardous waste disposal as per pharmacy SOPs; a record will be kept by pharmacy of what is sent for disposal and reported to the Sponsor if requested.

A 5% excess of patient packs will be manufactured in case a participant loses or damages their medication. If a replacement needs to be supplied, Sharp Clinical Services will advise which spare pack should be used, according to their copy of the randomisation schedule.

Participants will be advised to keep the IMP at room temperature.

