13.2 Analysis plan

A detailed statistical analysis plan (SAP) will be developed and finalised prior to the locking of the trial database in consultation with the trial steering committee.

We will conduct an intention-to-treat analysis (all randomised participants) and per-protocol analysis (completing participants with 75% compliance).

Primary endpoint:

Urine NTX at six months in postmenopausal osteopenic or osteoporotic women with baseline serum selenium below 120 mcg/l

Baseline data will be assessed for comparability between the treatment groups. NTX/Cr will be assessed visually for normality and if it is non-Normal a log-transform will be applied, with results reported as percentage difference between geometric means. Analysis of covariance (ANCOVA) will be used to compare mean NTX/Cr between the groups adjusting for baseline NTX/Cr measurements. The Hochberg procedure will be used to account for multiple comparisons; P-values are ordered from smallest to largest. If the largest P-Value is less than 0.05 then all null hypotheses can be

rejected. If not, if the second P-value is less than 0.05/2, then all bar the largest can be rejected, and so on (SA Julius, An Introduction to Statistics in Early Phase Trials).

Secondary endpoints:

Urine NTX at three months: analysis as described for the primary endpoint

Serum selenium, SePP, serum CTX, PINP, osteocalcin, thyroid function, glucose and insulin at three and six months: analysis as described for the primary endpoint.

BMD by DXA at six months: analysis as described for the primary endpoint.

We will examine impact of baseline selenium levels on the NTX response to selenium supplementation by fitting a linear model with NTX at follow-up as the dependent variable and baseline selenium, baseline NTX and dose as independent variables. With n=66 (receiving active treatment) the minimum correlation that can be detected with 90% power and 5% significance level is 0.44.

Short physical performance battery, grip strength, hydroperoxidases, glutathione peroxidase activity, highly sensitive CRP, IL-6 analysis as described for the primary endpoint.

There is no planned interim analysis of outcome measures. There will be an interim analysis of baseline serum selenium to determine the final sample size.

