16.3 Consent

The PI retains overall responsibility for the informed consent of participants at their site and will ensure that any person delegated responsibility to participate in the informed consent process is duly authorised, trained and competent to participate according to the ethically approved protocol, principles of Good Clinical Practice (GCP) and Declaration of Helsinki.

Consent will be obtained by a doctor or specialist research nurse with appropriate training and experience assessed and delegated by the PI

This study will not include vulnerable participants or participants who lack capacity.

Informed consent will be obtained prior to the participant undergoing any trial procedures.

Each prospective participant will receive a participant information sheet giving details of the study and will have at least 24 hours to consider their participation in the study. All participants will also be given a verbal explanation of the information in the PIS and the opportunity to ask questions before the first visit, during the consent process and throughout the duration of the study. The consent process will follow the Sheffield CRF SOP for informed consent.

Where a participant is able to consent but later becomes incapacitated, they will be withdrawn from the study. Data obtained up to that point will be retained and used in analysis. This is specified in the PIS.

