20. WITHDRAWAL

Participants will be withdrawn at the participant's request, if they have a serious adverse reaction, if they develop diabetes or thyroid dysfunction, if they lose capacity, if they require treatment with medication on the prohibited list or if they develop any new medical problems which would render the study measurements invalid.

If IMP is stopped, and if the participant is willing, wherever possible they will be asked to continue to complete study assessments unless the PI judges this to be inappropriate due to the participant's health or personal circumstances. This decision will be documented in the CRF and site file, reported to the DMEC and included in the final study report.

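### Section 11.10 withdraws women from the trial for missing the three-month safety bloods, where stopping the study drug would be enough and would keep their six-month urine NTX

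*Protocol*

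**What the plan says.** Section 11.10 sets two rules. Low capsule compliance has no effect on follow-up: "Patients with less than 75% compliance will continue in the trial and ITT analysis". Non-compliance with the three-month safety monitoring is treated differently, and the rule reads "do not attend or decline to have blood test) will be withdrawn from the trial".

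Section 20 gives the reasons for withdrawal: the participant's request, then "if they have a serious adverse reaction, if they develop diabetes or thyroid dysfunction, if they lose capacity", then a need for prohibited medication or a new medical problem that would invalidate the measurements. Missed safety monitoring is not named. The next paragraph says "If IMP is stopped, and if the participant is willing, wherever possible they will be asked to continue to complete study assessments", with an exception where the PI judges this inappropriate.

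Section 13.2 commits to the full randomised population: "We will conduct an intention-to-treat analysis (all randomised participants". The primary endpoint is urine NTX at six months (section 9), and section 10.1 describes its collection: "Urine samples will be obtained as triplicate samples from fasted second morning voids". Drug is supplied in two bottles, the first at baseline and "the second bottle of 93 tablets at the 13 week visit" (section 11.5).

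**The concern.** Stopping unmonitored drug is a sound safety rule. Taking the woman out of the trial goes further than that rule needs. Taken at its word, section 11.10 has the site stop collecting the primary endpoint from randomised women because of something that happened after randomisation, namely avoiding a visit or a blood draw. Nothing shows that this is related to treatment or tolerability, but it could be. An analysis plan can model values that were never collected; it cannot recover them. This works against the commitment in section 13.2 to analyse everyone randomised.

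Part of the loss is avoidable. Many women who do not attend at 13 weeks would be lost whatever the protocol says. A woman who attends and only declines venepuncture can still supply urine at 26 weeks, at a visit already in the schedule.

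**Working it through.** **The text side by side**

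- Section 11.10 acts on trial participation and does not mention section 20.
- The follow-up clause in section 20 is triggered by the drug being stopped. A woman withdrawn under section 11.10 would get no second bottle, so the trigger is arguably met, but the reader has to infer this.
- Section 11.7 shows that the protocol can speak of stopping treatment alone when that is meant. Section 11.10 does not use that wording.

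**Inputs**

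- Section 13.1: target difference 10 nmol BCE/mmolCr, SD 12.5, correlation between baseline and six months 0.7, two-sided 2.5% level, 90% power, 21 per group required, 33 per group recruited.
- Section 8: expected loss to follow-up under 10%, about 3 of 33. This is total loss, so it serves only as an upper bound for this group.
- Section 10.3: 13-week window day 73 to 94; 26-week window day 172 to 187.
- Assumed, because the protocol gives no figure: 1 to 3 of 33 missing, all from one arm, with six-month NTX 0.5 to 1 residual SD away from those who stay.

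**Reproducing the stated sample size**

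- Residual SD after baseline adjustment = 12.5 × √(1 − 0.7²) = 8.93.
- Normal approximation: n = 2 × (2.241 + 1.282)² × 8.93² / 10² = 19.8, so 20 per group.
- Noncentral t with 2n − 3 degrees of freedom: 22 per group.
- The stated 21 lies between the two and is accepted.

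**Possible shift if the women are lost**

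Standard error of an arm difference at 33 per arm = 8.93 × √(2/33) = 2.20. With k women missing from one arm, lying m residual SDs from those who stay, the arm mean shifts by (k/33) × m × 8.93.

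| k | m | Shift (nmol BCE/mmolCr) | Shift / standard error |
|---|---|---|---|
| 1 | 0.5 | 0.14 | 0.06 |
| 2 | 1 | 0.54 | 0.25 |
| 3 | 1 | 0.81 | 0.37 |

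The largest shift is about 8% of the 10 nmol target (0.81/10).

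**Power (noncentral t, two-sided 2.5%)**

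- Difference 10: 98.7% at 33 per arm and 97.7% at 30 per arm.
- Difference 9, the figure section 13.1 derives from its regression coefficient: 96.2% and 94.3%.

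**Price of keeping the women in**

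- If drug stops between day 73 and day 94, the time off drug at the 26-week visit runs from 172 − 94 = 78 days to 187 − 73 = 114 days.
- Worst case, with no drug effect left in k of 33 women in an active arm: dilution = 10 × k/33 = 0.30, 0.61 or 0.91 nmol for k = 1, 2 or 3.
- Power at a difference of 10 − 0.91 = 9.09 with 33 per arm: 96.5%.

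**The case against.** The strongest reply is that section 20 already deals with this. It uses the word for withdrawal in one paragraph and, in the next, asks willing women whose drug is stopped to stay for assessments. Its list of reasons is not said to be complete, so an omitted reason is not a contradiction. This largely stands: a reasonable reading covers most of these women. What remains is that section 11.10, the rule staff would apply on the day, says something stronger and does not point to section 20.

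The two rules in section 11.10 are also not inconsistent. Poor capsule compliance bears on efficacy and missed glucose and thyroid tests bear on safety, so different consequences for dosing are reasonable. That stands too. The point concerns follow-up only.

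The size rests on assumptions. No rate is given, nothing in the protocol suggests that refusal of blood depends on treatment, and blinding makes loss from one arm alone less plausible. The largest shift avoided (0.81 nmol) is no bigger than the largest dilution accepted (0.91 nmol). The case therefore rests on the ITT principle and on low cost, not on a demonstrated gain in accuracy. The dilution is not bias under a treatment-policy comparison, and section 20 already accepts it for other women who stop the drug.

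Two further inferences are tempting and should not be drawn:

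- Section 16.3, on loss of capacity, says "Data obtained up to that point will be retained and used in analysis". A reader might take this as proof that withdrawal always ends data collection. It is specific to women who can no longer consent and says little about a capable woman who declines one test.
- Sections 12 and 20 withdraw women with new diabetes or thyroid dysfunction, where section 11.7 stops treatment. A reader might see the same fault there. Section 20 already provides for their follow-up, so nothing needs to change.

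**Conclusion.** The point holds as a wording fault with a small possible effect on the primary endpoint. Read literally, section 11.10 gives up six-month urine NTX that could still be collected, and the safety purpose does not require this. A reader might infer that the protocol definitely discards these women's data, or that the primary result is at risk. The document supports neither: section 20 can be read to keep the women in, and under the assumed range (1 to 3 of 33, one arm only, 0.5 to 1 residual SD) the arm mean shifts by about 0.1 to 0.8 nmol, at most 0.37 standard errors, in an unknown direction. Power stays above 94% at either planning difference with 30 per arm. Severity is low, and the change is worth making because it is cheap.

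**What to change.** In section 11.10, replace withdrawal from the trial with: IMP is stopped (the second bottle is not dispensed) and, if willing, the participant is asked to continue study assessments as in section 20, including the 26-week urine NTX. In section 20, add missed or declined three-month safety bloods as a reason for stopping IMP.

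The cost is one reworded sentence and one added reason. The visits are already scheduled, and the analysis model, analysis set and sample size stay as they are. The safety protection is kept, since no further drug is given without monitoring. A few women will contribute NTX measured about 78 to 114 days off drug. The ITT comparison takes on that dilution, at most about 0.9 nmol.

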11.11 NIMP

To ensure vitamin D sufficiency, all participants will be given a single bolus dose of colecalciferol 100,000IU at the screening visit. The colecalciferol will be bulk supplied by STH pharmacy to the Clinical Research Facility and stored in a locked drug cupboard, solely for use in this study. A stock list will be maintained with the stored supply. The colecalciferol will be prescribed by the PI or delegated doctor on a day case prescription chart, and administered by the doctor or specialist research nurse. The administration will be recorded on the day case prescription and in the participant case report form.

At the request of the REC committee that approved this trial, there will be an additional bottle of open label placebo capsules released from SHARP. This will be the 'practice placebo'; volunteers will be shown the capsules during the screening visit and offered the opportunity to try taking a placebo capsule if they are concerned about their ability to swallow them. These placebo capsules will be released from SHARP to STH pharmacy and STH pharmacy will supply the full bottle for storage in the Clinical Research Facility. A drug accountability log will be kept to track usage and disposal of each capsule. This will also be recorded on the participant case report form.

12. RISKS AND BENEFITS

We recognise that in moving from an association study to a clinical trial there is a risk that the trial will be negative. For example, in cross-sectional studies of the effect of a diet rich in fruit and vegetables it appeared there was a benefit to bone (30), but this wasn't confirmed in an RCT (31). However, because selenium supplementation could be an effective, inexpensive, and well-tolerated option for a group with unmet clinical need, we think that the proof of concept from our association study justifies moving forward to an RCT rather than repeated observational studies.

There have been RCTs of selenium in other disease areas so we already have some estimate of dose and safety. Studies have investigated the effect of selenium supplementation on a range of other health outcomes including cognition, immune function, cancer, cardiovascular function, diabetes, fertility and reproduction (8).

Selenium is used routinely for Graves' thyroid ophthalmopathy (GO) without side effects or effect on thyroid status at doses of 200 mcg/day for six months (32, 33). The UK GO guidelines recommend that selenium can be initiated by general practitioners or hospital general physicians, and no monitoring of selenium levels or other safety measures is required during the six month course (34).

We plan to administer selenium at a maximum dose of 200 mcg per day. The Institute of Medicine upper level for selenium is 400 mcg/day, which is 2.5 times below the No Observed Adverse Effect Level (35). Therefore the risk of adverse effects in this study is very low.

There is a published incident of selenium poisoning in 227 people due to mislabelling of a supplement product in the USA. The median dose of selenium was 41,585 mcg/day for 30 days. On questioning 201 people had symptoms of toxicity (nausea and vomiting, brittle nails, hair loss, joint pain, fatigue, irritability and garlic-like taste), 118 had sought medical advice for their symptoms, but only one patient required hospitalisation, and none died (36).

We will ask participants about symptoms of toxicity at each study contact.

We will measure serum selenium concentration at screening, baseline, three months and six months to evaluate the magnitude of effect of the study doses on serum selenium levels. The available data suggest that the optimum serum selenium concentration is 130 to 150 mcg/l, and nearly everyone in the UK has serum selenium concentrations below this range (8). The population range of serum selenium in the USA is 80 to 200 mcg/l. We expect that a dose of 200mcg/day will increase serum selenium by an average of 90mcg/l so the number of women whose serum selenium might increase above 200mcg/l is small.

Selenium has a role in thyroid function. There is a reported association of high blood selenium with type 2 diabetes, although this was not confirmed in a prospective study with doses of 100 to 300 mcg/day for 6 months (19). We will exclude volunteers with diabetes or thyroid dysfunction at screening, and measure thyroid function, fasting glucose and insulin at screening/baseline, three months and six months. We will withdraw participants who develop thyroid dysfunction or diabetes during the study. We will analyse between-group differences in change in thyroid function tests and blood glucose as a secondary endpoint.

The data on serum selenium concentration, glucose, thyroid function and any possible symptoms of toxicity will be reviewed by the DMEC.

The study procedures (DXA bone densitometry, blood and urine sampling and muscle function tests) carry negligible risks to the participants.

The radiation dose has been assessed by a Radiation Protection Supervisor and Clinical Radiation Expert.

13. STATISTICS

13.1 Power calculation

A 20% (10nmol BCE/mmolCr) decrease in urine NTX is a plausible and clinically significant effect size.

In a previous study, 200mcg daily for six months increased serum selenium by 90mcg/L (19).

In our observational study of serum selenium and bone turnover markers, the regression coefficient of serum selenium and NTX/Cr was -0.101 (9), so if the relationship were causative we would expect an increase in serum selenium of 90mcg/L to be associated with a reduction in urine NTX/Cr of 9 nmol BCE/mmolCr (approximately 20%).

In support of this estimate, we would not expect as large a change in bone turnover as would be seen with a potent anti-resorptive drug such as a bisphosphonate (about 60%), but it might be

similar to a weaker anti-resorptive such as a SERM. In a study of six months' treatment with the SERM lasofoxifene (37), NTX decreased by 29%. We have also used this study as a model for the likely SD (12.5) and the correlation between NTX/Cr at baseline and six months (0.7).

A 20% decrease in NTX is clinically significant; a 20% decrease in NTX (about 1 standard deviation decrease) with bisphosphonate treatment is associated with a 30% decrease in incident vertebral fracture (38).

To achieve 90% power to detect this mean difference at the 2.5% (two-sided) level will require 21 patients per group. To allow for dropout, group imbalance and the secondary endpoint analyses we will recruit 33 patients per group with serum selenium below 120mcg/l (99 patients in total).

We will not exclude women with baseline serum selenium above 120mcg/l, because it is important that the results of this study are generalisable into practice, but it is possible that there will be no benefit in women who are selenium replete at baseline. Therefore we will recruit enough participants to ensure that at least 99 women with baseline serum selenium below 120mcg/l are randomised for the primary endpoint analysis. We will determine the total number required from an interim analysis of the distribution of baseline serum selenium in the first 40 women recruited. In our previous cross-sectional study, 80% of European women had serum selenium below 120mcg/l, so we expect that we will need to recruit 120 in total. If at the interim analysis, less than 60% of women recruited have serum selenium below 120 mcg/l, the study recruitment strategy will be reviewed and discussed with the funder to determine if the trial should proceed. Therefore the maximum sample size will be 165 (if 60% of women have serum selenium below 120mcg/l)

We will conduct a secondary analysis of all participants to determine whether baseline serum selenium is a determinant of bone turnover response.

The power calculation was done by [name], statistician at the Sheffield School of Health and Related Research (ScHaRR).

